14.2 Efficacy evaluation data			
14.2.1 Primary and secondary efficat	cy variables		
Table 14.2.1.1 - Efficacy variables, ove	rview of key results (Efficacy Analysis	Set)	
Table 14.2.1.2 - Change from baseline	in Creatinine-normalised u-LTE4 by Vi	isit, summary statistics (Efficacy Analysis Se	et)
Figure 14.2.1.1 - Change from baseline	in Creatinine-normalised u-LTE4 by	/isit, mean(SD) (Efficacy Analysis Set)	
Table 14.2.1.3 - Analysis of Change fro	m baseline in Creatinine-normalised u	I-LTE4 at Week 4, MMRM (Efficacy Analysis	Set)
Table 14.2.1.3.1 - Analysis of Change f	rom baseline in Creatinine-normalised	u-LTE4 at Week 4, sensitivity analysis, MM	IRM (Efficacy Analysis Set) (optional
Table 14.2.1.4 - Analysis of Change fro	m baseline in Creatinine-normalised u	I-LTE4 at Week 12, MMRM (Efficacy Analysi	is Set)

Table 14.2.1.4.1 - Analysis of Change from baseline in Creatinine-normalised u-LTE4 at Week 12, sensitivity analysis, MMRM (Efficacy Analysis Set) (optional)

Figure 14.2.1.2 - Analysis of Change from baseline in Creatinine-normalised u-LTE4, MMRM at Week 4 and Week 12 - Forest plot (Efficacy Analysis Set)

Table 14.2.1.5 - Change from baseline in CFVR by Visit, summary statistics (Efficacy Analysis Set)

Figure 14.2.1.3 - Change from baseline in CFVR by Visit, mean(SD) (Efficacy Analysis Set)

Table 14.2.1.6 - Analysis of Change from baseline in CFVR at Week 4, MMRM (Efficacy Analysis Set)

Table 14.2.1.6.1 - Analysis of Change from baseline in CFVR at Week 4, sensitivity analysis, MMRM (Efficacy Analysis Set) (optional)

Table 14.2.1.7 - Analysis of Change from baseline in CFVR at Week 12, MMRM (Efficacy Analysis Set)

Table 14.2.1.7.1 - Analysis of Change from baseline in CFVR at Week 12, sensitivity analysis, MMRM (Efficacy Analysis Set) (optional)

Figure 14.2.1.4 - Analysis of Change from baseline in CFVR, MMRM at Week 4 and Week 12 - Forest plot (Efficacy Analysis Set)

Table 14.2.1.8 - Change from baseline in LAD resting mean diastolic flow velocity by Visit, summary statistics (Efficacy Analysis Set)

Figure 14.2.1.5 - Change from baseline in LAD resting mean diastolic flow velocity by Visit, mean(SD) (Efficacy Analysis Set)

Table 14.2.1.9 - Analysis of Change from baseline in LAD resting mean diastolic flow velocity at Week 4, MMRM (Efficacy Analysis Set)

Table 14.2.1.10 - Analysis of Change from baseline in LAD resting mean diastolic flow velocity at Week 12, MMRM (Efficacy Analysis Set)

Figure 14.2.1.6 - Analysis of Change from baseline in LAD resting mean diastolic flow velocity, MMRM at Week 4 and Week 12 - Forest plot (Efficacy Analysis Set)

Table 14.2.1.11 - Change from baseline in LAD hyperaemic flow velocity by Visit, summary statistics (Efficacy Analysis Set)

Figure 14.2.1.7 - Change from baseline in LAD hyperaemic flow velocity by Visit, mean(SD) (Efficacy Analysis Set)

Table 14.2.1.12 - Analysis of Change from baseline in LAD hyperaemic flow velocity at Week 4, MMRM (Efficacy Analysis Set)

Table 14.2.1.13 - Analysis of Change from baseline in LAD hyperaemic flow velocity at Week 12, MMRM (Efficacy Analysis Set)

Figure 14.2.1.8 - Analysis of Change from baseline in LAD hyperaemic flow velocity, MMRM at Week 4 and Week 12 - Forest plot (Efficacy Analysis Set)

Table 14.2.1.14 - Change from baseline in LVEF at rest by Visit, summary statistics (Efficacy Analysis Set)

Figure 14.2.1.9 - Change from baseline in LVEF at rest by Visit, mean(SD) (Efficacy Analysis Set)

Table 14.2.1.15 - Analysis of Change from baseline in LVEF at rest at Week 4, MMRM (Efficacy Analysis Set)

Table 14.2.1.16 - Analysis of Change from baseline in LVEF at rest at Week 12, MMRM (Efficacy Analysis Set)

Distribution:

Original:

Copy:

TPCA025 Version 2 (based on TPQA036 Version 2)

Effective Date: 27th August 2017 Prior Effective Date: 21st December 2016

Sponsor:	AstraZeneca AB	Protocol/CIP Number:	D7550C00003		
CIL Project Number:	40343				
Figure 14.2.1.10 - Analysis of Change from b Table 14.2.1.17 - Change from baseline in LV Figure 14.2.1.11 - Change from baseline in L Table 14.2.1.18 - Analysis of Change from ba	4-GLS at rest by Visit, summary stat V-GLS at rest by Visit, mean(SD) (E	istics (Efficacy Analysis Set) ifficacy Analysis Set)	Analysis Set)		
Table 14.2.1.19 - Analysis of Change from ba					
Figure 14.2.1.12 - Analysis of Change from b			cy Analysis Set)		
Table 14.2.1.20 - Change from baseline in LV					
Figure 14.2.1.13 - Change from baseline in L					
Table 14.2.1.21 - Analysis of Change from ba	seline in LV-GLS at hyperaemia at	Week 4, MMRM (Efficacy Analysis Set)			
Table 14.2.1.22 - Analysis of Change from ba	seline in LV-GLS at hyperaemia at	Week 12, MMRM (Efficacy Analysis Set)			
Figure 14.2.1.14 - Analysis of Change from ba	aseline in LV-GLS at hyperaemia, N	IMRM at Week 4 and Week 12 - Forest plo	t (Efficacy Analysis Set)		
Table 14.2.1.23 - Change from baseline in LV	GCS at rest by Visit, summary sta	tistics (Efficacy Analysis Set)			
Figure 14.2.1.15 - Change from baseline in L	V-GCS at rest by Visit, mean(SD) (I	Efficacy Analysis Set)			
Table 14.2.1.24 - Analysis of Change from ba					
Table 14.2.1.25 - Analysis of Change from ba					
Figure 14.2.1.16 - Analysis of Change from b					
Table 14.2.1.26 - Change from baseline in LV					
Figure 14.2.1.17 - Change from baseline in L					
Table 14.2.1.27 - Analysis of Change from ba	a contra la se la co	en e a casa anti mendiane "-	TOTAL STREET, S		
Table 14.2.1.28 - Analysis of Change from ba Figure 14.2.1.18 - Analysis of Change from ba Set)					
Table 14.2.1.29 - Individual plasma concentra					
Table 14.2.1.30 - Summary of plasma concer		inalysis set)			
14.2.2 Exploratory variables - cfPWV/bPW/					
Table 14.2.2.1 - Change from baseline in cfP	na a malimulan and areas	e s - caner Ben Brandan e Su			
Table 14.2.2.2 - Analysis of Change from bas		AND A DESCRIPTION OF A			
Table 14.2.2.3 - Analysis of Change from bas					
Table 14.2.2.4 - Analysis of Change from bas Table 14.2.2.5 - Analysis of Change from bas					
14.2.3 Exploratory variables - Quality of life		MINITAL PALADICS (LINCACY F	dialysis dely		
Table 14.2.3.1 - Change from baseline in Qua		Overall Scores by Visit summary statistics	(Efficacy Analysis Set)		
Table 14.2.3.2 - Change from baseline in SF-			(Emodo) / Maijsis ocij		
Table 14.2.3.3 - Analysis of Change from bas			alysis Set)		
Table 14.2.3.4 - Analysis of Change from bas					
14.2.4 Exploratory variables - GRACE2.0 s					
Table 14.2.4.1 - GRACE 2.0 score at baseline	e, summary statistics (Efficacy Anal	ysis Set)			
14.2.5 Exploratory variables - Cardiovascu Table 14.2.5.1 - Change from baseline in Car		nmary statistics (Efficacy Analysis Set)			
Table 14.2.5.2 - Analysis of Change from bas	eline in Cardiovascular biomarkers	at Week 4, MMRM - NORMAL variables (E	fficacy Analysis Set)		
Table 14.2.5.3 - Analysis of Change from bas	eline in Cardiovascular biomarkers	at Week 4, MMRM - log-NORMAL variable	s (Efficacy Analysis Set)		
Table 14.2.5.4 - Analysis of Change from baseline in Cardiovascular biomarkers at Week 12, MMRM - NORMAL variables (Efficacy Analysis Set)					
Table 14.2.5.5 - Analysis of Change from baseline in Cardiovascular biomarkers at Week 12, MMRM - log-NORMAL variables (Efficacy Analysis Set)					
14.3 Safety evaluation data					
14.3.1 Exposure					
Table 14.3.1.1 - Duration of exposure - Coho					
Figure 14.3.1.1 - Exposure over time - Cohort	4 weeks treatment and Cohort 12	weeks treatment (Safety Analysis Set)			
14.3.2 All adverse events	Cohod (works treatment and	Cabad 12 usaka trastruart. On trastruart	(Osfatu analusia Cat)		
Table 14.3.2.1 - Adverse events in any categored Table 14.3.2.2 - Adverse events in any categored Table 14.3.2.3 - Adverse events, most common	ory - Cohort 4 weeks treatment and	Cohort 12 weeks treatment - Off treatment	(Safety analysis Set)		
Set) Table 14.3.2.4 - Adverse events, most comm					
Set) Table 14.3.2.5 - Adverse events by system of Analysis Set)					
Distribution	: Orig	inal: (Copy:		
TPCA025 Version 2 (based on TPQA036 Version 2)			ve Date: 27 th August 2017 Date: 21 st December 2016		

CONFIDENTIAL AND PROPRIETARY

Sponsor:	AstraZeneca AB	Protocol/CIP Number:	D7550C00003
CIL Project Number:	40343		

Table 14.3.2.6 - Adverse events by system organ class and preferred term - Cohort 4 weeks treatment and Cohort 12 weeks treatment - Off treatment (Safety

Analysis Set) Table 14.3.2.7 - Adverse events, by preferred term and maximum reported intensity - Cohort 4 weeks treatment and Cohort 12 weeks treatment - On treatment (Safety Analysis Set)

Table 14.3.2.8 - Adverse events, by preferred term and maximum reported intensity - Cohort 4 weeks treatment and Cohort 12 weeks treatment - Off treatment (Safety Analysis Set)

Table 14.3.2.9 - Adverse events, by preferred term and investigator's causality assessment - Cohort 4 weeks treatment - On treatment (Safety Analysis Set) Table 14.3.2.10 - Adverse events, by preferred term and investigator's causality assessment - Cohort 12 weeks treatment - On treatment (Safety Analysis Set)

Table 14.3.2.11 - Adverse events, by preferred term and investigator's causality assessment - Cohort 4 weeks treatment - Off treatment (Safety Analysis Set)

Table 14.3.2.12 - Adverse events, by preferred term and investigator's causality assessment - Cohort 12 weeks treatment - Off treatment (Safety Analysis Set)

Table 14.3.2.13 - Adverse events with outcome of death, by system organ class and preferred term - Cohort 4 weeks treatment and Cohort 12 weeks treatment -On treatment (Safety Analysis Set)

Table 14.3.2.14 - Adverse events with outcome of death, by system organ class and preferred term - Cohort 4 weeks treatment and Cohort 12 weeks treatment -Off treatment (Safety Analysis Set)

Table 14.3.2.15 - Adverse events with outcome of death, causally related to study treatment - Cohort 4 weeks treatment and Cohort 12 weeks treatment - On treatment (Safety Analysis Set) Table 14.3.2.16 - Adverse events with outcome of death - Cohort 4 weeks treatment and Cohort 12 weeks treatment - key subject information (Safety Analysis

Set)

Table FDAAA1-1 - Non-serious adverse events occurring in greater than 5% of subjects - Cohort 4 weeks treatment and Cohort 12 weeks treatment - On Trable FDAAA1-2 - Non-serious adverse events occurring in greater than 5% of subjects - Cohort 4 weeks treatment and Cohort 12 weeks treatment - Off

treatment (Safety Analysis Set)

14.3.3 Deaths

Table 14.3.3.1 - All deaths - Cohort 4 weeks treatment and Cohort 12 weeks treatment - On treatment (Safety Analysis Set)

Table 14.3.3.2 - All deaths - Cohort 4 weeks treatment and Cohort 12 weeks treatment - Off treatment (Safety Analysis Set)

14.3.4 Serious adverse events

Table 14.3.4.1 - Serious adverse events, by system organ class and preferred term - Cohort 4 weeks treatment and Cohort 12 weeks treatment - On treatment (Safety Analysis Set)

Table 14.3.4.2 - Serious adverse events, by system organ class and preferred term - Cohort 4 weeks treatment and Cohort 12 weeks treatment - Off treatment (Safety Analysis Set) Table 14.3.4.3 - Serious adverse events, causally related to study treatment - Cohort 4 weeks treatment and Cohort 12 weeks treatment - On treatment (Safety

Table 14.3.4.4 - Serious adverse events - Cohort 4 weeks treatment and Cohort 12 weeks treatment - key subject information (Safety Analysis Set)

14.3.5 Discontinuation of investigational product due to adverse events

Table 14.3.5.1 - Adverse events leading to discontinuation of investigational product, by system organ class and preferred term - Cohort 4 weeks treatment and Cohort 12 weeks treatment - On treatment (Safety Analysis Set)

Table 14.3.5.2 - Adverse events leading to discontinuation of investigational product, causally related to study treatment - Cohort 4 weeks treatment and Cohort 12 weeks treatment - On treatment (Safety Analysis Set) Table 14.3.5.3 - Adverse events leading to discontinuation of investigational product - Cohort 4 weeks treatment and Cohort 12 weeks treatment - key subject

information (Safety Analysis Set) Table 14.3.54 - Adverse events leading to investigational product interrupted, by system organ class and preferred term - Cohort 4 weeks treatment and Cohort 12 weeks treatment - On treatment (Safety Analysis Set)

14.3.6 Other significant adverse events

NA

14.3.7 Clinical laboratory evaluation

Table 14.3.7.1 - Haematology, coagulation and clinical chemistry laboratory variables over time (Safety Analysis Set)

Table 14.3.7.2 - Haematology, coagulation and clinical chemistry laboratory variables, baseline to maximum value during treatment - Cohort 4 weeks treatment (Safety Analysis Set)

Table 14.3.7.3 - Haematology, coagulation and clinical chemistry laboratory variables, baseline to maximum value during treatment - Cohort 12 weeks treatment (Safety Analysis Set) Table 14.3.7.4 - Haematology, coagulation and clinical chemistry laboratory variables, baseline to minimum value during treatment - Cohort 4 weeks treatment

(Safety Analysis Set) Table 14.3.7.5 - Haematology, coagulation and clinical chemistry laboratory variables, baseline to minimum value during treatment - Cohort 12 weeks treatment (Safety Analysis Set)

Table 14.3.7.6 - Urinalysis variables over time (Safety Analysis Set)

Table 14.3.7.7 - Urinalysis, baseline versus maximum value on treatment, shift table - Cohort 12 weeks treatment (Safety Analysis Set)

Table 14.3.7.8 - Maximum on-treatment ALT and AST by maximum total bilirubin for assessing Hy's Law criteria - Cohort 4 weeks treatment (Safety Analysis Set) Table 14.3.7.9 - Maximum on-treatment ALT and AST by maximum total bilirubin for assessing Hy's Law criteria - Cohort 12 weeks treatment (Safety Analysis Set)

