The total number of patients that will be randomized in the study has been increased from 100 to approximately 138. The reason for increasing the total number of patients is to make sure that there are enough patients to evaluate the sustained effect on CFVR after 12 weeks, that is, about 33 evaluable patients per arm for AZD5718 [REDACTED] and placebo. An evaluable patient is defined as a patient with a valid CFVR measurement at Visit 2 (baseline), and one postbaseline visit as judged by the CFVR Core lab. The total number of patients for evaluation of uLTE₄ and CFVR at week 4 will be more than 33 patients per high-dose and

placebo arm (exact number will be known at the unblinding at the end of the trial). This is due to the fact that patients that are already randomized to the study (approximately 38) will have a treatment period of 4 weeks while future randomized patients (approximately 100) will have a treatment period of 12 weeks.

Section 1.4 (Study Design) has been updated to reflect this change, however, the updated numbers are reflected in all relevant sections of the CSP.

Interim analysis

The interim analysis is updated as follows: The text is revised to alter the futility interim analysis to two administrative interim analyses for internal decision making. The futility analysis has been removed to be able to evaluate the sustained effect on u-LTE₄ at 12 weeks. The focus of the study extended to 12 weeks aiming on evaluation 5-LO pathway inhibition, ie not only at the end of 4 weeks but at the end of 12 weeks to ensure the use of the drug in a chronic setting. The futility analysis has therefore been changed into two administrative interim analyses for internal decision making. In the event of positive outcome at any of the administrative interim analyses an evaluation of exposure-response relationship may be performed. This is reflected in the Study Synopsis (Statistical methods) and Section 8.5.6 (Interim analysis).

Biomarker sampling

An additional biomarker sample will be collected at day 2 after the ACS.

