8.8.3 Clinical Laboratory Evaluations

Clinical laboratory evaluation is performed based on the Safety Analysis Set. The list and the assessment of all Clinical Laboratory variables are reported section 6.6.3.

Laboratory test results for haematology, coagulation and clinical chemistry

Laboratory test results for haematology, coagulation and clinical chemistry will be summarized in AZ preferred units for each treatment group, and for change from baseline at each visit. Change from baseline to each post-baseline visit will be calculated as the postbaseline visit value minus the baseline visit value.

Classification of the laboratory values with respect to the normal reference range will be provided (low/normal/high). Shifts from baseline to maximum/minimum value during Ontreatment phase of this classification will be presented for each treatment group and by cohort of patients.

Hy's law criteria will also be summarized in a double-entry table by cohort of patients.

Distribution:

Original:

Copy:

TPCA025 Version 2 (based on TPQA036 Version 2) Effective Date: 27th August 2017 Prior Effective Date: 21st December 2016

Sponsor:	AstraZeneca AB	Protocol/CIP Number:	D7550C00003
CIL Project Number:	40343		

Laboratory test results for urinalysis

Laboratory test results for quantitative variables (i.e. creatinine and albumin) will be summarized in AZ preferred units for each treatment group, and for change from baseline at each visit. Change from baseline to each post-baseline visit will be calculated as the post-baseline visit value minus the baseline visit value.

Shifts from baseline to maximum value during On-treatment phase will be presented for semi-quantitative variables (i.e. albumin, protein, blood, glucose and Leukocytes). All laboratory data for haematology, coagulation, clinical chemistry and urinalysis will be also presented in listings.

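### The only final urinalysis shift table in the SAP output list (14.3.7.7) is restricted to the 12-week cohort, although SAP 8.8.3 plans these shifts without a cohort limit

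*SAP*

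**What the plan says.** SAP 8.8.3 works in the Safety Analysis Set and treats urinalysis in two parts.

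- Measured quantities: "Laboratory test results for quantitative variables (i.e. creatinine and albumin) will be summarized" by treatment group and visit.
- Graded results: "Shifts from baseline to maximum value during On-treatment phase will be presented for semi-quantitative variables (i.e. albumin, protein, blood, glucose and Leukocytes").

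Neither part names a cohort. Earlier in the same section, the blood laboratory shifts and the Hy's Law table are explicitly to be shown by cohort. SAP 7.9 says that outputs combine the 4-week and 12-week cohorts unless something else is specified.

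The output list under heading 14.3.7 has two urinalysis tables:

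- "Table 14.3.7.6 - Urinalysis variables over time (Safety Analysis Set"), with no cohort in the title;
- Table 14.3.7.7, "Urinalysis, baseline versus maximum value on treatment, shift table - Cohort 12 weeks treatment (Safety Analysis Set").

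No urinalysis shift table is listed for the 4-week cohort or for both cohorts together.

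On cohort sizes, the Protocol version history says: "The total number of patients that will be randomized in the study has been increased from 100 to approximately 138". It adds that "patients that are already randomized to the study (approximately 38) will have a treatment period of 4 weeks" and that "future randomized patients (approximately 100) will have a treatment period of 12 weeks".

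**The concern.** Programmers build the study report from the output list. If they follow it literally, the final shift summary for dipstick protein, blood, glucose and leukocytes, and for albumin where it is graded, will contain only patients randomized under the 12-week design. Urinalysis is a named safety variable (Protocol 8.4.2), and the analysis text gives no reason to treat the earlier cohort differently. A reader of the report could not compare the arms on these shifts for the 4-week patients and would not be told why they are missing.

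**Working it through.** **1. Size of the cohort affected.** Inputs are from the Protocol version history: about 138 randomized in total, about 100 under the 12-week design.

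- 138 − 100 = 38, which reproduces the stated figure of about 38.
- 38 / 138 = 27.5%.
- At exact 2:1:2 allocation: 38 × 2/5 = 15.2, 38 × 1/5 = 7.6, 38 × 2/5 = 15.2, so roughly 15, 8 and 15 by arm.

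**2. Do these patients have the data?** Yes. The assessment schedule (Protocol 4.1, Table 1) has urine safety samples at Visits 2, 3 and 4. Protocol 1.4 limits only Visits 4b and 4c to patients included under the amendment. A 4-week patient therefore has a scheduled baseline and two scheduled on-treatment samples, which is enough for a baseline-to-maximum shift.

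**3. Comparison of the listed final tables.**

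| Output | 4-week cohort | 12-week cohort |
|---|---|---|
| Blood laboratory, shift to maximum | 14.3.7.2 | 14.3.7.3 |
| Blood laboratory, shift to minimum | 14.3.7.4 | 14.3.7.5 |
| Urinalysis, shift to maximum | none | 14.3.7.7 |
| Hy's Law | 14.3.7.8 | 14.3.7.9 |
| ECG, shift to last on-treatment value | 14.3.8.4 | 14.3.8.5 |

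The numbering runs 14.3.7.6, 14.3.7.7, 14.3.7.8 without a gap, so no table has dropped out of the list.

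**4. Is a 12-week-only table usual in this SAP?** Two other tables carry that label alone, 14.1.5 (demographics) and 14.1.7 (subject characteristics). Each stands beside a table without a cohort restriction, 14.1.4 and 14.1.6. Table 14.3.7.7 has no such partner.

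**5. Is the restriction declared?** No. Protocol 8.5.3 plans urinalysis shifts for all patients. SAP 5.2 records one change to that analysis, which concerns the categories used for the shift. It does not mention leaving out a cohort.

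**The case against.** A reader might infer that the dipstick results of the 4-week cohort are summarised nowhere. The documents do not support that, for four reasons.

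- **Interim output.** SAP 8.10.3 plans the same graded urinalysis shifts at both interim analyses without a cohort limit, and up to Visit 4 at the first. SAP 8.10 places the first analysis after at least 45 patients have a Visit 4 CFVR measurement. The 4-week patients were randomized first, so many of them should be included. This is a planned summary, but an unblinded interim one and not a final table.
- **Table 14.3.7.6.** Its title covers the whole Safety Analysis Set. SAP 8.8.3 describes the by-visit summary for creatinine and albumin but does not say that nothing else may be shown. SAP 7.1 provides for all safety variables to be summarised by group and visit where appropriate, so dipstick counts might appear there. The title does not settle it. Counts by visit would in any case not be a shift from baseline to the on-treatment maximum.
- **Albumin.** SAP 6.6.3 allows albumin to be quantified or graded. Quantified albumin is in the over-time summary for both cohorts, so only graded albumin is affected.
- **Listings.** SAP 8.8.3 promises listings of all urinalysis data. These preserve the values but do not compare treatment groups.

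The remedy is also open to argument. SAP 8.8.3 asks for a split by cohort for blood laboratory shifts but not for urinalysis shifts. With the joint default in SAP 7.9, the text points to one pooled urinalysis table at least as well as to a pair.

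These points narrow the finding. They do not explain why the only final urinalysis shift table excludes a cohort that the analysis text includes.

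**Conclusion.** The output list and the analysis text disagree. As listed, the final tables would omit the dipstick shifts of the 4-week cohort, contrary to SAP 8.8.3 and the default in SAP 7.9. The pattern of the neighbouring tables and the silence of SAP 5.2 suggest an oversight, though the documents do not state the intention.

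The size is about 38 of 138 patients (27.5%). This is a planning figure for randomized patients; SAP 7.9 defines the cohort by when patients were randomized and gives no number. The split of about 15, 8 and 15 assumes that the early cohort was allocated exactly 2:1:2. That many of these patients appear in the first interim output is likely from the order of enrolment but is not stated.

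This is a minor reporting inconsistency. It changes no hypothesis test, alpha, power or sample size.

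**What to change.** Do one of the following before the final tables are programmed:

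- remove the 12-week restriction from Table 14.3.7.7 so that it covers both cohorts, which fits SAP 7.9 and 8.8.3 without an additional table; or
- add a 4-week companion table, as is done for the blood laboratory and ECG shifts.

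In either case, state in SAP 8.8.3 whether Table 14.3.7.6 includes the dipstick variables. If the restriction was intended, say so with the reason in SAP 8.8.3 and 5.2.

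The cost is at most one more run of a planned table program and a sentence or two of text. No new data are needed.
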